12.4 OCULAR ADVERSE EVENT BY FIXED AND FLEXIBLE ADMINISTRATION

Overall and by-cycle ocular adverse event, corneal adverse events, and ocular adverse events leading to implant removal will be analyzed by flexible or fixed dosing regimen subgroup. Other ocular adverse events by the subgroup may be performed on as-needed basis.

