11.0 SAFETY ANALYSES

All safety analyses will be performed using the safety population. Unless otherwise stated, the last non-missing safety assessment before the SLT treatment (Day 1) will be used as the baseline for all analyses of that safety parameter. As indicated in Section 6.4, safety data collected at Screening for eligibility assessment will not be analyzed.

All safety analyses described in the section 11.0 will be performed both Bim SR 10 µg and Bim SR 15 µg.

Ocular safety will be evaluated through; ocular AEs, best corrected visual acuity, visual field examination, specular microscopy, macroscopic iris color assessment, macroscopic conjunctival hyperemia assessment, gonioscopy/angle assessment, biomicroscopy (using a slit lamp), lens assessment, optic disc examination, dilated ophthalmoscopy, pachymetry, and anterior segment-optical coherence tomography.

Non-ocular safety analysis includes non-ocular adverse events (AEs), clinical laboratory results, vital signs (blood pressure, pulse rate and temperature), and pregnancy test results.

Safety analyses will be summarized by study periods. Analysis study periods are defined as follows:

- **During the study:** Date of SLT treatment through Month 24/Exit visit/last study visit available.
- **Analysis Cycle 1:** SLT Treatment date (Day 1) through the second Bim SR administration date – 1. If the second Bim SR administration was not given to a patient, all safety assessments through Month 24/Exit visit/last study visit available will be included in analysis cycle1.
- **Analysis Cycle 2:** Second Bim SR administration date through Month 24/Exit visit – 1.
- **Analysis Cycle 3:** Third Bim SR administration date through Month 24/Exit visit – 1, valid for only Bim SR 15 µg.

All summaries will be based on the first treatment received in each eye (Bim SR or SLT). If a patient who received both SLT and Bim SR in the same eye, safety assessments will be summarized in Bim SR. For non-ocular safety measures, overall summaries will be presented regardless of study treatment. For ocular safety assessments, summaries will be presented for the periods of during the study, Analysis Cycle 1 and Analysis Cycle 2 as shown in Figure 11-1 below.

Figure 11-1 Analysis Cycle Illustration

| Treatment Schedule | Cycles for Safety Data Analyses | |
|--|---------------------------------|------------------|
| | SLT eye | BIM SR eye |
| Day 1, SLT administration | Analysis Cycle 1 | Analysis Cycle 1 |

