11.1 ADVERSE EVENTS

Adverse events will be coded by system organ class and preferred term using the Medical Dictionary for Regulatory Activities, version 22.0 or newer.

An AE will be considered a treatment-emergent adverse event (TEAE) for the study treatment period if the AE meets one of the following criteria:

- The onset date is on or after the first study treatment date.
- The onset date is before the first study treatment date and either:
 - The severity of the event worsened on or after the first treatment date.
 - The event became serious on or after the first study treatment date.

An AE will be considered as a TEAE for a treatment cycle if the AE meets one of the following criteria:

- The onset date is on or after the treatment administration of the cycle but prior to the next cycle administration.
- The onset date is before the treatment administration of the cycle and either:
 - The severity of the event worsened on or after the treatment administration of the cycle.
 - The event became serious on or after the treatment administration of the cycle.

An ocular AE will be defined by the location information on the adverse event page in eCRF.

An overall summary of patient incidences of TEAEs will be presented by event type and event category (ocular or non-ocular). These summaries will include the following:

- All TEAEs
 - Ocular
 - Non-ocular
- Treatment-related TEAEs:
 - Ocular
 - Related to study drug
 - Related to study drug administration procedure
 - Related to SLT laser
 - Non-ocular
- Treatment-related serious TEAEs:

- Ocular
 - Related to study drug
 - Related to study drug administration procedure
 - Related to SLT laser
- Non-ocular
 - Any TEAEs leading to Bim SR implant removal
 - Any TEAEs leading to study discontinuation
 - Deaths

The following non-ocular TEAEs will be summarized by SOC and PT:

- Any non-ocular TEAEs,
- Any treatment related non-ocular TEAEs,
- Any serious non-ocular TEAEs, and
- Any non-ocular TEAEs leading to study discontinuation.

Ocular TEAEs will be summarized by analysis cycle and by treatment eye as described below:

- Any ocular TEAEs by PT
- Any ocular TEAEs by SOC, PT, and severity
- Any treatment related ocular TEAEs by SOC and PT
- Any serious ocular TEAEs by SOC and PT
- Any ocular TEAEs leading to study discontinuation by SOC and PT
- Any ocular TEAEs within two days of study treatment by SOC and PT

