The KM analyses will be performed for each of the first *confirmed* ECL and the first *observed* ECL. Compelling evidence of intra-eye variability of CECD has been observed in global, well-controlled, randomized, multicenter studies despite methodological measures in place to control for CECD variability. Therefore, the key analysis for Time to ECL Event will be based on the confirmed ECL values. For each analysis, Time (days) is calculated as follows:

- Time to the First *Confirmed* ECL event = (Date of the First *Confirmed* ECL event – Date of the First Study Treatment) + 1,
- Time to the First *Observed* ECL event = (Date of the First *Observed* ECL event – Date of the First Study Treatment) + 1,

where the Date of First Study Treatment is the first date of Bimatoprost SR 10 µg or SLT administration. For eyes that did not have any observed ECL events, time to the first ECL event will be right-censored at the last available CECD assessment date.

For each scheduled visit, the tabulation will display the number of eyes at risk, cumulative number of eyes with events, and the cumulative probability of event and the associated 95% confidence interval.

Exposure Adjusted Analysis for ECL Rate

Additionally, to take into account the differences in follow up time, an exposure-adjusted analysis for ECL rate over the entire study period will be performed by treatment for Bimatoprost SR 10 µg and SLT treated eyes. Exposure time will be calculated for each treated eye. For eyes that experienced an ECL event during the study, exposure time is the number of days from the first study treatment administration to the date when the first ECL event occurred. For eyes without an ECL event, exposure time is the number of days from the first study treatment administration to the last assessment for CECD. Exposure time in person-years is calculated as (exposure time in days)/365.25. Exposure adjusted ECL rate will be calculated per 100 person-years as:

- $100 \times (\text{number of eyes that experienced the ECL event}) / \text{total exposure time in person-years for the treatment group}$.

Listings for patients with $\geq 20\%$ CECD loss at any visit will be provided.

Coefficient of Variation Average (CV_{AVE}): Coefficient of variation average of raw data and changes from baseline will be summarized descriptively by visit and analysis cycle for each eye.

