If both scheduled and unscheduled visit occur within a single window, the scheduled visit will be used; and unscheduled visits will be used only if there are no scheduled values available in that window. If multiple visits are eligible for windowing within a single visit window, the scheduled visit closest to target day will be used in the analysis.

If 2 visits are equidistant to the target day, the later visit will be used.

Table 17-2 Visit Windows for By Visit Analysis for Assessments Occurring Every 4 weeks

| Derived Visit | Target Visit Day* | Visit Window* |
|-----------------------------------|---|---|
| Baseline ^a | -1 | ≤ (SLT Date -1) |
| Analysis Cycle 1 | | |
| Cycle 1 SLT Day 1 | 1 | SLT Date |
| Cycle 1 Bim SR Day 1 ^b | Bim SR 1st administration, Day 1 | Bim SR 1st administration, Day 1 |
| Cycle 1 Bim SR Day 2 ^b | Bim SR 1st administration, Day 1 + 1 | Bim SR 1st administration Day 1 + 1 |
| Cycle 1 Week 4 | 25 | [Bim SR 1st administration, Day 1+2, 38] |
| Cycle 1 Week 8 | 53 | [39, 66] |
| Cycle 1 Week 12 | 81 | [67, 91] |
| Cycle 1 Week 15 | 102 | [92,119] |
| Cycle 1 Week 20 | 137 | [120, 150] |
| Cycle 1 Week 24 | 165 | [151, 178] |
| Cycle 1 Week 28 | 193 | [179, 203] |
| Cycle 1 Week 31 | 214 | [204, 231] |
| Cycle 1 Week 36 | 249 | [232, 262] |
| Cycle 1 Week 40 | 277 | [263, 290] |
| Cycle 1 Week 44 | 305 | [291, 315] |
| Cycle 1 Week 47 | 326 | [316, 343] |
| Cycle 1 Week 52 | 361 | [344,373] |
| Cycle 1 Month 13 ^c | 387 | [374,401] |
| Cycle 1 Month 14 | 417 | [402,431] |
| Cycle 1 Month 15 ^c | 447 | [432,461] |
| Cycle 1 Month 16 | 477 | [462,506] |
| Cycle 1 Month 18 | 537 | [507,566] |
| Cycle 1 Month 20 | 597 | [567,626] |
| Cycle 1 Month 22 ^c | 657 | [627,686] |
| Cycle 1 Month 24 | 717 | >686 |
| Analysis Cycle 2 ^d | | |
| Cycle 2 Bim SR Day 1 | 1 | Bim SR 2nd administration, Day 1 |
| Cycle 2 Bim SR Day 2 | 2 | Bim SR 2nd Administration Day 1 + 1 |
| Cycle 2 Week 4 | 29 | [Bim SR 2nd administration, Day 1+2, 42] |
| Cycle 2 Week 8 | 57 | [43, 70] |
| Cycle 2 Week 12 | 85 | [71, 98] |
| Cycle 2 Week 16 | 113 | [99,126] |
| Cycle 2 Week 20 | 141 | [127,154] |
| Cycle 2 Week 24 | 169 | [155, 182] |
| Cycle 2 Week 28 | 197 | [183,210] |
| Cycle 2 Week 32 | 225 | [211, 238] |
| Cycle 2 Week 36 | 253 | [239, 266] |

| | | |
|-------------------------------|--|---|
| Cycle 2 Week 40 | 281 | [267, 294] |
| Cycle 2 Week 44 | 309 | [295, 322] |
| Cycle 2 Week 48 | 337 | [323,350] |
| Cycle 2 Week 52 | 365 | [351, 377] |

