| Cycle 2 Month 13 | 391 | [378, 405] |
| Cycle 2 Month 14 | 421 | [406,435] |
| Cycle 2 Month 15 | 451 | [436,465] |
| Cycle 2 Month 16 | 481 | [466,495] |
| Cycle 2 Month 17 | 511 | [496, 525] |
| Cycle 2 Month 18 | 541 | [526,555] |
| Cycle 2 Month 19 | 571 | [556,585] |
| Cycle 2 Month 20 | 601 | > 585 |
| Analysis Cycle 3 ^e | | |
| Cycle 3 Bim SR Day 1 | Bim SR 3rd administration, Day 1 | Bim SR 3rd administration, Day 1 |
| Cycle 3 Bim SR Day 2 | Bim SR 3rd administration Day 1 + 1 | Bim SR 3rd administration Day 1 + 1 |
| Cycle 3 Week 4 | 29 | [Bim SR 3rd administration, Day 1+2, 42] |
| Cycle 3 Week 8 | 57 | [43, 70] |
| Cycle 3 Week 12 | 85 | [71, 98] |
| Cycle 3 Week 16 | 113 | [99,126] |
| Cycle 3 Week 20 | 141 | [127,154] |
| Cycle 3 Week 24 | 169 | [155, 182] |
| Cycle 3 Week 28 | 197 | [183,210] |
| Cycle 3 Week 32 | 225 | [211, 238] |
| Cycle 3 Week 36 | 253 | [239, 266] |
| Cycle 3 Week 40 | 281 | [267, 294] |
| Cycle 3 Week 44 | 309 | [295, 322] |
| Cycle 3 Week 48 | 337 | [323,350] |
| Cycle 3 Week 52 | 365 | [351, 377] |
| Cycle 3 Month 13 | 391 | [378, 405] |
| Cycle 3 Month 14 | 421 | [406,435] |
| Cycle 3 Month 15 | 451 | [436,465] |
| Cycle 3 Month 16 | 481 | > 465 |

* Target days and window definitions from Week 4 and onward are based on the relative days from the date of the Bim SR administration for each cycle.

^a Relative to the date of the SLT administration.

^b Relative to the date of Bim SR 1st administration. If a patient did not receive the first Bim SR, but treated in SLT at Day 1, Bim SR 1st administration, Day 1 will be determined as SLT+ 3 days.

^c Patients who received the second administration of Bim SR at W16 and patients who never received a second administration may skip the visits.

^d Relative to the date of the second Bim SR administration.

^e Relative to the date of the third Bim SR administration and valid for Bim SR 15 µg.

Table 17-3 Visit windows for By Visit and Analysis Cycle for Assessments Occurring Every 3- 4 Months

| Derived Visit | Target Visit Day* | Visit Window* |
|---|--|---|
| Baseline ^a | -1 | ≤ (SLT Date -1) |
| Analysis Cycle 1 | | |
| Cycle 1 SLT Day 1 | 1 | SLT Date |
| Cycle 1 Bim SR 1 st Day 1 ^b | Bim SR 1 st administration, Day 1 | Bim SR 1 st administration, Day 1 |
| Cycle 1 Week 4 ^c | 25 | [Bim SR 1 st administration, Day 1+ 1, 52] |
| Cycle 1 Week 12 | 81 | [53, 122] |
| Cycle 1 Week 24 | 165 | [123, 220] |
| Cycle 1 Week 40 | 277 | [221,318] |

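### By-cycle percentages of late-onset ocular and corneal adverse events depend on cycle length, which runs from about 16 weeks to 24 months and differs between the fixed and flexible regimens

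*SAP*

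**What the plan says.** SAP 11.0 defines the safety periods by administration dates. Cycle 1 is "SLT Treatment date (Day 1) through the second Bim SR administration date" minus one day. If there is no second implant, "all safety assessments through Month 24/Exit visit/last study visit available will be included in analysis cycle1". Cycle 2 is "Second Bim SR administration date through Month 24/Exit visit" minus one day. SAP 11.1 counts an event towards a cycle if it starts on or after that cycle's administration and before the next one, with no window of fixed length.

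On reporting, SAP 11.1 states that "Ocular TEAEs will be summarized by analysis cycle and by treatment eye". The measure is patient incidence there, and number and percent in Protocol 7.3.4. SAP 12.4 adds, by regimen subgroup, that "Overall and by-cycle ocular adverse event, corneal adverse events, and ocular adverse events leading to implant removal will be analyzed".

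Under SAP 4.0 and 12.0, fixed-regimen patients were to be retreated at Week 16. The flexible subgroup includes patients retreated at Week 16, later but before Month 12, or never.

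For endothelial cell loss (ECL) the SAP takes a further step. Section 11.3.5 plans, "to take into account the differences in follow up time, an exposure-adjusted analysis for ECL rate", and 12.3 repeats that analysis by regimen. Sections 11.1 and 12.4 contain nothing equivalent for adverse events.

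**The concern.** Because a cycle ends at the next implant or at study exit, its length is set by when, or whether, the patient is retreated. The longer an eye stays in a cycle, the more late events that cycle collects, even if the risk per unit time never changes. The regimens differ in just this respect: a flexible group holds more patients with a long Cycle 1.

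Two comparisons that readers will naturally make are exposed: first implant against second implant, and fixed against flexible retreatment. Late events matter here. Protocol 1.2 expects polymer degradation to take about 12 months, and corneal events are singled out in both 11.1 and 12.4.

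**Working it through.** **Document figures.** The documents give no adverse-event rate, so there is none to reproduce. The cycle lengths can be taken from the definitions in SAP 11.0 and the target days in SAP 17.3, Table 17-2, which count from the relevant implant: "Cycle 1 Month 24 | 717 | >686" and "Cycle 2 Month 20 | 601 | > 585".

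| Period | Situation | Days used | Source |
|---|---|---|---|
| Cycle 1 | retreated at Week 16 | 108 | 112 − 4, from the first implant on Day 4 |
| Cycle 1 | never retreated | 717 | Month 24 target day |
| Cycle 2 | retreated at Week 16 | 609 | 717 − 108 (Month 20 target day 601, open-ended window) |
| Cycle 2 | retreated near Month 12 | 357 | 717 − 360 |

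Cycle 1 formally starts three days before the first implant, at SLT; this changes nothing of substance.

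**Assumptions.** The late-event hazard h is constant and identical in every patient. The values of h and the retreatment shares are assumed, because the documents give neither.

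**Formula.** Incidence = 1 − exp(−h × days / 365.25).

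With h = 0.2 per eye-year:

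- Cycle 1, 108 days: 1 − exp(−0.0591) = 5.7%
- Cycle 1, 717 days: 1 − exp(−0.3926) = 32.5%
- Flexible group, half never retreated and half retreated at Week 16: (5.7 + 32.5)/2 = 19.1%
- Cycle 2, 609 days: 1 − exp(−0.3335) = 28.4%
- Cycle 2, 357 days: 1 − exp(−0.1955) = 17.8%

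At the same hazard, a fixed patient's Cycle 2 shows 28.4% against 5.7% in Cycle 1.

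**Range over the hazard** (half of the flexible group never retreated):

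| h per eye-year | Fixed, Cycle 1 | Flexible, Cycle 1 |
|---|---|---|
| 0.1 | 2.9% | 10.4% |
| 0.2 | 5.7% | 19.1% |
| 0.4 | 11.2% | 32.8% |

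**Range over the share never retreated** (h = 0.2, the rest retreated at Week 16), using (1 − share) × 5.74 + share × 32.47:

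- 20%: 11.1%
- one third: 14.7%
- 50%: 19.1%
- 80%: 27.1%

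If 10% of fixed patients also miss the second implant (assumed), their figure rises from 5.7% to 0.9 × 5.74 + 0.1 × 32.47 = 8.4%, which narrows the gap.

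**Does a rate repair it?** Only for late events. Suppose 20% of eyes have an event at the procedure and none later, identically in both regimens. The crude Cycle 1 figure is 20% in both. Events per 100 eye-years to first event become:

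- Fixed: 20 / (0.8 × 108/365.25) = 84.5
- Flexible, half never retreated, mean 412.5 days: 20 / (0.8 × 412.5/365.25) = 22.1

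Now add a constant late risk of 5% per 112 days to the 20% at the procedure, and compare 112 with 717 days:

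| Measure | 112 days | 717 days |
|---|---|---|
| All events, crude | 24.0% | 42.4% |
| All events, per 100 eye-years | 100.4 | 31.7 |
| Late events alone, crude | 5.0% | 28.0% |
| Late events alone, per 100 eye-years | 16.7 | 16.7 |

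So the crude percentage misleads for late events, the all-event rate misleads when events cluster at the procedure, and the rate restricted to late events does neither.

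**The case against.** The strongest reply is that a flat hazard does not describe these events. Protocol 1.2.3 reports that in the phase 1/2 study most adverse events arose within two days of administration and were attributed to the procedure. For such events the crude Cycle 1 percentage is the same whatever the cycle length. SAP 11.1 also already separates ocular events within two days of treatment from those after two days, and the first of these tables gives every administration an equal window. All of this stands, and it confines the point to late-onset events. The after-two-days table runs to the next administration, so it keeps the problem.

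Several stronger readings are tempting and should be resisted:

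- A reader might infer that every by-cycle percentage is out by a factor of about three. The illustration covers late events only, under an assumed hazard and split.
- A reader might infer that Bim SR versus SLT is biased. Both eyes of a patient share the same cycle boundaries (SAP Figure 11-1), so it is not.
- A reader might infer that the overall tables share the defect. At the final lock, planned follow-up is 24 months in both regimens. Actual follow-up could differ at the earlier locks, but that is not a matter of cycle length.
- A reader might infer that all comparisons should move to exposure-adjusted rates. The working shows that this can create a spurious gap in the opposite direction.

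It is also fair to say that fixed versus flexible is a non-randomised, descriptive split with no planned test, and that 12.4 does not itself mention percentages; that measure comes from 11.1 and Protocol 7.3.4.

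**Conclusion.** The point holds for ocular and corneal events that start more than two days after administration, in the by-cycle tables and in those tables split by regimen. Planned time at risk in Cycle 1 varies by a factor of 717/108 = 6.6, and in Cycle 2 by 609/357 = 1.7. At an assumed hazard of 0.2 per eye-year, identical risk shows as 5.7% against 32.5% for the extreme Cycle 1 lengths, and as 5.7% against 11.1% to 27.1% for a fixed group all retreated at Week 16 against a flexible group with 20% to 80% never retreated. These sizes rest on assumed hazards and shares, on nobody being retreated between Week 16 and Month 12, and on a constant hazard after day 2. Fixed patients who missed the second implant shrink the gap.

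The SAP accepts the principle for ECL in the same two subgroups, so the omission for late adverse events is inconsistent. It touches no primary or formally tested result, and correcting it is a worthwhile, low-cost improvement.

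**What to change.** Keep the planned percentages. In SAP 11.1 and 12.4:

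- For the after-two-days ocular table and the corneal events table, by cycle, eye and regimen, add the number of eyes with an event per 100 eye-years at risk. A common fixed window after each administration is an acceptable alternative.
- Compare procedure-related events between cycles and regimens through the existing within-two-days table, produced by regimen as well.
- State that crude by-cycle percentages for late events are not to be compared across cycles or regimens, and that all-event comparisons are not to be based on rates.

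The cost is one new derived variable and a few columns. Exposure must run from cycle start to event onset or cycle end. The ECL exposure in 11.3.5 cannot be reused, because it covers the whole study and stops at the ECL event or the last cell-density assessment. The rates still assume a roughly constant hazard after day 2; the common-window option does not need that assumption, but it ignores events after the window closes.

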13.0 VISUAL FUNCTION QUESTIONNAIRE

National Eye Institute Visual Function Questionnaire-25 responses collected at Baseline will not be summarized as part of this SAP.

14.0 INTERIM ANALYSES

No interim analysis is planned for the study. Three database locks are planned for this study as described in Section 4.0. The analysis results based on the first database lock is considered as the primary analysis. The analyses based on the Month 12 and/or final database locks will provide further efficacy and safety information. Three CSRs will be written, one following each lock.

15.0 DETERMINATION OF SAMPLE SIZE

The sample size calculation is based on paired-eye differences using a normal approximation with a 2-sided significance level of 0.05, assuming that there is no difference in mean IOP change from baseline between Bim SR 10 µg eyes and SLT eyes, and that change from baseline in IOP has a standard deviation of 4 mmHg. A sample size of 144 patients with eyes treated with Bim SR 10 µg and SLT will provide approximately 98% power in showing noninferiority in 3 out of 3 timepoints with a noninferiority margin of 1.5 mm Hg, and 90% power in showing noninferiority in 2 out of 3 timepoints with a noninferiority margin of 1.0 mmHg, assuming that both the between-eyes and the within-patient correlation coefficients are 0.5.

Assuming a premature discontinuation rate of 10%, approximately 160 patients are to be enrolled into this study and treated with Bim SR 10 µg. Additionally, there are 55 Bim SR 15 µg treated patients who were enrolled before implementation of Amendment 3 and treated with the 15 µg Bim SR dose strength.

16.0 STATISTICAL SOFTWARE

Statistical analyses will be performed using version 9.4 (or newer) of SAS software.

17.0 DATA HANDLING CONVENTIONS

17.1 EFFICACY DATA

As stated in protocol Section 4.5.2 Prohibited Medications/Treatments, eye(s) may receive non-study IOP lowering medication or procedure. To avoid confounding of efficacy data, IOP measurements obtained after initiating the use of non-study IOP-lowering medication or procedure in an eye will be treated as missing for that eye unless specified otherwise.

For sensitivity analyses, missing data will be imputed using the last observation carried forward (LOCF) and multiple imputation method as detailed in Section 17.2.

17.2 MISSING DATA HANDLING FOR SENSITIVITY ANALYSES

17.2.1 Last Observation Carried Forward (LOCF)

Last observations carried forward method will be used to impute missing IOP data up to Week 24. In this approach, IOP data after the rescue treatment will be replaced by LOCF.

